#### 4.7 RNA isolation

RNA will be extracted from cultured organoids using Trizol reagent (Life Technologies, Carlsbad, CA), according to the manufacturer's instructions. 1 µg of total RNA will be reverse transcribed using the VILO kitrandom hexamerssynthesisystem (Life Technologies, Carlsbad, CA). Gene expression will be assessed by quantitative real-time PCR (RT-qPCR) using an ABI 7500 Fast thermal cycler (Life Technologies, Carlsbad, CA) and SYBR Green chemistry (Fast SYBR Green Master Mix; Life Technologies, CA). All reactions will be performed in triplicate.

#### 4.8 Characterization of the activation state of human hepatic stellate cells

Quiescent hepatic stellate cells accumulate 80% of retinol as retinyl palmitate in lipid droplets in the cytoplasm, and can release it depending on the extracellular retinol state (18). However, following liver injury, stellate cells can become activated, proliferate, lose retinol droplets, and secrete extracellular matrix (ECM), becoming myofibroblast-like cells. In this activated state, they may be responsible for the progression of liver disease to fibrosis (19).

In stellate cells isolated from patients we will evaluate the expression of genes involved in fibrogenic processes, such as collagen-1,  $\alpha$ -smoothmuscleactin (-SMA), transforminggrowthfactor (TGF)  $\beta$ 1, tissueinhibitormatrixmetalloproteases (TIMP) andmatrixmetalloprotease (MMP) 13 in order to investigate its activation status and evaluate any differences determined by the variants of PNPLA3.

However, stellate cells do not release retinol or its metabolites only during fibrogenic processes, but also during regenerative processes, such as after partial hepatectomy (20). In fact, these cells possess enzymes for the storage and metabolism of retinol. Retinol acquired from outside is preferentially stored as retinyl esters of retinol by an enzyme lecithin retinol acyl-transferase (LRAT) using acyl-CoA, or fromretinol acyltransferase (ARAT) in the case of quiescent cells (21). Retinol can then be metabolised into retinaldehyde by alcohol dehydrogenase (ADH) and subsequently be converted to retinoic acid (RA) by retinaldehyde dehydrogenase (RALDH) (22).

To better understand retinol metabolism in stellate cells isolated from patients with different PNPLA3 genotypes, we will investigate the expression of genes such as LRAT, ARAT, ADH and RALDH, involved in retinol storage and release.

Furthermore, depending on their activation state, stellate cells can regulate the progression of liver disease also by supporting inflammatory processes, producing cytokines, chemokines and/or

by directly interacting with T cells, natural killer (NK) and NKT cells (23). Therefore, we will also investigate the expression of these genes that contribute negatively or positively to the resolution of liver damage in assembloids.

## 5. ENDPOINTS

### 5.1 Primary Endpoints

1. Isolation of epithelial cells in order to generate models of the main populations of liver cells in a three-dimensional culture environment, called organoids, and molecular characterization of the generated models. Isolation of stellate cells and their phenotypic and molecular characterization. Generation of assemblyloids that mimic the hepatic tissue architecture and its phenotypic and molecular characterization to study the onset and development of steatohepatitis.
2. Evaluation of the impact of the I148M variant (evaluation of possible combinations both in epithelial cells - hepatocytes and in stellate cells) on the steatohepatitic phenotype in human liver assembloids, with particular reference to:
  - Lipid accumulation in hepatocytes (quantitative and qualitative analysis)
  - Lipotoxicity and expression of inflammatory markers (gene expression)
  - Activation of fibrogenesis (assessment of the activation state of stellate cells, retinol metabolism and extracellular matrix deposition)

Steatohepatitis will be defined in the simultaneous presence of all these alterations in the assemblage.

3. Analysis of variants of the TM6SF2, MBOAT7 and GCKR genes, previously correlated with the development of non-alcoholic steatohepatitis (14).

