#### 4.5 Treatment in vitro

It has recently been shown that the addition of oleate and palmitate to the culture medium is able to increase the formation of lipid droplets in hepatocytes and primary stellate cells, simultaneously causing a down-regulation of the expression of PNPLA3. Conversely, in the absence of retinol and palmitate, a reduction in intracellular lipid content and an increase in the expression of PNPLA3 (7).

The generated assemblyloids will be treated for 36 or 120 hours with oleic acid and palmitic acid (300  $\mu$ M both) (Sigma Aldrich, St Louis, MO). Treatments with the addition of cholesterol, fructose, insulin and low concentrations of ethyl alcohol will also be tested to mimic a condition of dysmetabolism, unbalanced diet and the main environmental determinants of liver disease. This experiment will allow us to evaluate differences in the accumulation and subsequent release of lipid droplets in cells with different genotypes of PNPLA3. After 36 hours, the lipid droplet content will be visualized by OilRed O histochemical staining. An analysis of stellate cell activation will also be performed after 36 hours. Instead, after 120 hours, the assemblyloids will be partly fixed in formaldehyde to analyze morphology, biomarkers and fibrotic status and partly frozen in liquid nitrogen for further gene expression analysis.

PNPLA3 will be silenced using antisense RNA (16)

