## 7. STATISTICAL ANALYSIS

### 7.1 Sample size and data analysis

The sample size was estimated in view of achieving the two primary outcomes of the project.

Previously published works (24, 25, 26, 27) have shown that the generation efficiency of liver organoids is approximately 100% starting from surgical resections and 33% from biopsies (24, 25).

Considering these estimates, in order to isolate at least 20 independent organoid cultures of each type of condition of interest in our study, we estimate to recruit at least 30 donors for each genetic variant. The intent is to obtain replicates for the analyses with a sufficient representation of the different stages of liver damage (normal liver, inflammation/fibrosis and hepatocellular carcinoma) and to be able to map the impact of the main most common inherited genetic variants (present in at least 20% of individuals) in the population.

For the first primary outcome, the primary analyses will be conducted from single-individual cell cultures. Given the descriptive nature of mapping cellular phenotypes and gene expression, and the large number of organoids ( $>10^3$ ) and cells ( $>10^9$ ) from a single individual, we will have sufficient statistical power (>80%) to identify and analyze specific cellular subsets representing >1% of the overall population.

As regards the second primary outcome, although there are important limitations in the estimate inherent to the type of project and linked to the uncertainty regarding the final characteristics of the model that will be developed during the project, we expect to observe a progressive increase in the

presence and severity of the steatohepatitis phenotype in organoids with increased number of PNPLA3 I148M variants. In particular, we estimated that we could reach a statistical power of 95% (alpha 0.05, two-tailed test) to observe a frequency of steatohepatitis phenotype of 75% vs. 25% in assemblyloids with extreme PNPLA3 genotypes, homozygous for the at-risk variant vs. wild-type (20 cases vs. 20 controls), which is consistent with the increased risk observed in clinical cohorts (28).

Statistical analyses will be performed using JMP (SA, Cary, NC) and R (<https://www.r-project.org>) software and statistical comparisons will be made using the one-way ANOVA or chi-square test, where appropriate. P values < 0.05 will be considered statistically significant.

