## 10. STUDIO MANAGEMENT

### 10.1 Data collection and management

Each participant will be assigned a unique code at enrollment. The file that associates the participant code with the participant identification data will be stored separately on a password-protected computer. The study database will be password-protected and uploaded to a password-protected computer and accessible only to study personnel designated by the principal investigator. De-identification of the data will be done in such a way that researchers accessing the database will not be able to trace the identity of the subjects in any way. Only local investigators will be able to trace the identity of the enrolled subjects.

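### The primary steatohepatitis call depends partly on human reading without cut-offs, and nothing in the available text keeps readers from knowing genotype or silencing arm

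*Protocol*

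**What the plan says.** Protocol 5.1 lists three components for the second primary endpoint. The first is "Lipid accumulation in hepatocytes (quantitative and qualitative analysis". The second is lipotoxicity and inflammatory markers, by gene expression. The third is activation of fibrogenesis, covering stellate-cell activation, retinol metabolism and extracellular matrix deposition. Steatohepatitis is called when all three are present together. No component has a positivity threshold.

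On the read-outs, section 4.5 says: "After 36 hours, the lipid droplet content will be visualized by OilRed O histochemical staining". Material fixed at 120 hours is examined for morphology, biomarkers and fibrotic status. Gene expression is by RT-qPCR in triplicate (4.7).

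Section 4.1 organises the cultures by genotype (CC, CG, GG). Section 7.1 expects a rise in the "presence and severity of the steatohepatitis phenotype in organoids with increased number of PNPLA3 I148M variants". It sizes the comparison for a "frequency of steatohepatitis phenotype of 75% vs. 25" per cent in assembloids "homozygous for the at-risk variant vs. wild-type (20 cases vs. 20 controls"), at a "statistical power of 95% (alpha 0.05, two-tailed test"). On the test it says "statistical comparisons will be made using the one-way ANOVA or chi-square test, where appropriate".

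The only coding described is in 10.1, where "researchers accessing the database will not be able to trace the identity of the subjects in any way". That concerns who the donor is. It does not concern genotype, fatty-acid load or silencing arm.

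**The concern.** Four features meet in one endpoint: part of the evidence is read by eye, no threshold anchors the reading, the groups are defined by genotype, and the expected direction is written down. If a reader knows the genotype, borderline cultures can be called positive more readily in GG and negative more readily in CC. That is differential misclassification. Unlike ordinary reading error it does not merely cost power; it moves the group difference towards the hypothesis.

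The same opening exists for the secondary endpoint on PNPLA3 silencing (section 5, Secondary Endpoints), where a benefit of silencing is also expected (section 2). Who reads specimens, and with what knowledge, is a matter of conduct settled before data exist, so it belongs in the protocol.

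**Working it through.** **Inputs from the protocol (7.1).** 20 vs 20, 75% vs 25%, two-sided alpha 0.05, chi-square test for the binary call, stated power 95%.

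**Assumptions, not in the protocol.** The common true rate p when genotype has no effect (50%, with 25% and 40% as checks). The misreading rate q: the share of true negatives in GG called positive and of true positives in CC called negative. Each culture counts as one independent call.

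**1. The plan's own figure.** Normal approximation with unpooled variance: SE = √(2 × 0.75 × 0.25 / 20) = 0.137. Power = Φ(0.50/0.137 − 1.96) = Φ(1.69) = 95.5%, which matches the stated 95%. Exact enumeration of the uncorrected chi-square test gives 90.1%.

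**2. Whole call movable.** Observed rates are GG = p + q(1 − p) and CC = p(1 − q). The chance of p < 0.05 is summed over all pairs of binomial outcomes. With p = 50%:

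| q | GG vs CC | Chi-square rejects | Fisher rejects |
|---|---|---|---|
| 0 | 50% vs 50% | 4.3% | 2.0% |
| 10% | 55% vs 45% | 8.4% | 4.7% |
| 20% | 60% vs 40% | 22.2% | 14.3% |
| 25% | 62.5% vs 37.5% | 32.8% | 22.8% |

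At q = 20% the chi-square figure is 23.7% for p = 40% and 29.1% for p = 25%. If only GG is misread, at q = 20% and p = 50%, it is 8.7%.

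**3. Only the lipid component movable.** Let L be the prevalence of lipid positivity and R = 0.50/L the chance that the other components are positive, taken as the same whatever the lipid status. Then GG = [L + q(1 − L)] × R and CC = L(1 − q) × R. With q = 20%:

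- L = 60%, R = 0.833: GG = 0.68 × 0.833 = 56.7%, CC = 0.48 × 0.833 = 40.0%; rejection 16.5%.
- L = 70%, R = 0.714: GG = 54.3%, CC = 40.0%; rejection 13.2%.
- L = 80%, R = 0.625: GG = 0.84 × 0.625 = 52.5%, CC = 0.64 × 0.625 = 40.0%; rejection 11.1%.

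**4. Small true difference.** With true rates of 55% vs 45%, the chance of significance without misreading is 8.4%. With q = 20% on the whole call, the rates become 0.55 + 0.20 × 0.45 = 64% and 0.45 × 0.80 = 36%, and the chance rises to 40.2%.

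**5. What misreading would not do.** Starting from 10/20 vs 10/20, a result of 13 vs 7 gives chi-square 3.60 (p = 0.058) and 14 vs 7 gives 4.91 (p = 0.027). Significance thus takes about 7 re-called cultures of 40. Reaching 75% vs 25% from 50% in both groups needs 5 re-calls per group, that is q = 50%.

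**6. Error unrelated to genotype.** Misreading 10% in both directions in both groups turns 75% vs 25% into 70% vs 30% and cuts exact power from 90.1% to 71.3%. That is loss of power, a different problem from the one raised here.

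**The case against.** The strongest objection is that the endpoint is less movable than a single stain score. All three alterations must be present, the lipotoxicity and inflammation component is RT-qPCR, and much of the stellate-cell and retinol work is gene expression too. A lipid reader can turn a culture positive only if the rest is already positive. This stands, and is why the 11–17% range is given beside the 22%. It does not remove the problem: with no thresholds, turning expression values into present or absent also takes judgement.

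A reader might infer that modest misreading could create the planned genotype effect. The figures do not support that. At 20% misreading the test still fails to reach significance in most runs, and 75% vs 25% would need half of the eligible calls to be wrong in both groups.

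A reader might also infer that the protocol has the laboratory that builds the cultures read them unmasked. It does not say so. Genotype comes from a separate blood assay (4.6), mixed epithelial and stellate combinations could be built from a coded list, and builders need not be readers. Nor does 5.1 say that the binary call uses the qualitative part of the lipid analysis. The protocol leaves these matters open. Part of the text after 3.1 was not available, so its silence can be judged only on the rest.

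Finally, bias here is not beyond repair: material fixed at 120 hours could in principle be re-read masked. That is a fallback, and 4.5 does not say whether the 36-hour stains are kept.

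**Conclusion.** The point holds as a gap in bias control for a primary endpoint. Nothing in the available text prevents readers from knowing genotype or silencing arm when they judge a call without thresholds in a comparison with a stated direction. With no true difference, 20% genotype-dependent misreading raises the rejection rate from 4.3% to about 11–17% through the lipid component alone and to 22% through the whole call. It can also make a small true difference look convincing.

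These sizes rest on an assumed misreading rate, an assumed true rate, an assumed lipid prevalence of 60–80%, independence of lipid status from the other components, and the uncorrected chi-square test; Fisher's test gives lower figures. No size was computed for the silencing comparison. The protocol does not show that misreading would occur. The case for change is that protection costs little.

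**What to change.** State in 4.5 and 5.1 that:

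- slides, images and RNA plates carry a random code with no genotype or silencing information, and no load condition where the stain does not itself reveal it (4.5 notes that fatty acids increase lipid droplets);
- existing staff read or quantify them without access to the key, against a positivity cut-off for each component fixed beforehand;
- each assembloid's steatohepatitis call is locked before the genotype file is linked.

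Staff who assemble the cultures may know genotype, provided readings are made on coded material. The participant coding in 10.1 can be extended to specimens. The cost is relabelling, holding the key separately and slightly slower feedback during model development. No additional patients, procedures or readers are needed.

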### Secondary Endpoints

- Knowledge of the behavioral and morphological differences between physiological and NASH hepatocytes and stellate cells.
  - Detection of new biomarkers predictive of the development and progression of the disease.
- a. - Analysis of epigenetic differences in physiological conditions, onset and progression of NASH.

- Knowledge of the molecular mechanisms underlying cellular-level observations using "omics" scale assessments and CRISPR-Cas9 genetic engineering.
- Analysis of the impact of PNPLA3 silencing on the steatohepatitis phenotype of human liver assembloids, stratified by I148M variant carrier status in epithelial cells vs. stellate cells.

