## FLOWCHARTS

| Period                             | Screening | Intervention |
|------------------------------------|-----------|--------------|
|                                    | (-t1)     | (t1)         |
| Enlistment                         |           |              |
| informed consent                   | -         |              |
| inclusion/exclusion criteria       | -         |              |
| Administration of the intervention |           |              |
| Biological sample collection       |           | -            |

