## 2.2 Secondary objectives

1. Identification of novel non-invasive biomarkers of pathological activation of human stellate cells and progression of liver damage to be subsequently validated in clinical series for future use in clinical management for individual risk stratification.
2. Study of epigenetic factors underlying the onset of non-alcoholic steatohepatitis and its progression to fibrosis, cirrhosis and HCC.
3. Evaluation of the impact of antisense oligonucleotides directed against PNPLA3 on the severity of the “steatohepatitic” phenotype (lipid accumulation, lipotoxicity and inflammation and fibrogenesis) in assembloids.

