## 3.2 Inclusion criteria

Patients of legal age who have given consent to participate in the study will be included and will be listed for the following procedures:

- liver biopsy for suspected nonalcoholic steatohepatitis (NASH) at the time of diagnosis;
- liver resection for hepatocellular carcinoma or other liver lesions (including secondary lesions from other neoplasms and benign focal lesions, which will allow obtaining starting liver tissue

healthy);

- post-transplant healthy liver biopsies;
- cholecystectomies.

You will also be required:

- willingness to sign informed consent for the study
- availability of DNA sample for genetic analysis and clinical data,
- blood sampling for genetic and epigenetic analysis and analysis of non-coding RNAs (lncRNAs, miRNAs and circRNAs).

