## 4. PROCEDURES RELATING TO THE STUDY

### 4.1 Intervention

In collaboration with the Liver Transplant Unit of the Foundation, samples of discarded tissue from patients undergoing liver resection will be collected (both intra-tumoral and extra-tumoral tissues in the case of hepatocarcinoma) or taken from the whole liver post-transplant. This procedure will not entail any additional risk for the patient compared to the usual routine, nor will it reduce the availability of material for standard pathological analyses.

These samples will allow us to isolate cells (ovalocytes – liver progenitor cells) to generate organoids from normal liver tissue (cholecystectomy) and suspected NASH.

We plan to collect up to 20 independent samples per tissue type. The groups considered will be:

- organoids, cultures of sinusoidal stellate cells isolated from 20 patients with CC genotype (I148I)
- organoids, cultures of sinusoidal stellate cells isolated from 20 patients with CG genotype (I148M)
- organoids, cultures of sinusoidal stellate cells isolated from 20 patients with GG genotype

(M148M)

A blood sample (approximately 7 cc) will also be taken, in addition to those already scheduled during regular clinical checks, at the time of surgery or liver biopsy.

It is planned to share a portion of the liver biopsy samples for immunohistochemical analysis to be carried out at the Division of Medicine, Institute for Liver and Digestive Health, University College London, in collaboration with [name], in order to further evaluate the expression of PNPLA3 associated with liver disease, subject to the preparation of an appropriate MTA.

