## 6. DURATION / TIMELINE OF THE STUDY

Study start month and year: 07/2021

Enrollment close month and year: 07/2024

Study end month and year: 07/2026

The study will last 60 months. In the first three years we expect to enroll approximately 60 subjects in accordance with the inclusion criteria.

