## 9. RISK/BENEFIT ASSESSMENT

The study does not foresee an immediate benefit for patients, but the results of this trial will have the potential to lead to a decoding of the mechanisms underlying the development of NASH, resolve the temporal order of events that regulate its evolutionary trajectory, understand its progression, characterization and improve the therapeutic management of patients.

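### A secondary endpoint promises predictive biomarkers, but each donor is sampled once with no later outcome, so in patients only cross-sectional association with stage can be shown

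*Protocol*

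**What the plan says.** The Secondary Endpoints list "Detection of new biomarkers predictive of the development and progression of the disease". The corresponding item in section 2.2 is narrower: "Identification of novel non-invasive biomarkers of pathological activation of human stellate cells and progression of liver damage", which are "to be subsequently validated in clinical series for future use in clinical management for individual risk stratification".

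On sampling, the flowchart has two columns, screening and a single intervention time t1, and the row "Biological sample collection" is marked only under t1. Section 4.1 adds a study blood sample of about 7 cc, taken "in addition to those already scheduled during regular clinical checks, at the time of surgery or liver biopsy". Section 3.2 ties this blood to genetic, epigenetic and non-coding RNA analyses. The same section admits donors having "liver biopsy for suspected nonalcoholic steatohepatitis (NASH) at the time of diagnosis", liver resection for hepatocellular carcinoma (HCC) or other lesions, biopsy of a healthy liver after transplant, or cholecystectomy.

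Section 6 closes enrolment in 07/2024 and ends the study in 07/2026.

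**The concern.** To show that a marker predicts development or progression, it must be measured before the event, and the event must then be observed in the same person. Here suspected-NASH donors are sampled when the disease is being diagnosed, HCC donors when the tumour is being removed, and nobody is followed afterwards. A blood RNA or epigenetic mark that differs between stages could be a cause of the disease, a consequence of it, or an effect of the setting in which the blood was drawn. The endpoint as worded would allow such a difference to be described as predictive.

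The setting matters because it partly follows stage. Suspected NASH is bled around a biopsy; HCC, other resected lesions and cholecystectomy are bled around surgery. If the draw falls before sedation or anaesthesia in some donors and after it in others, any effect of the procedure on circulating markers would be mixed with stage.

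**Working it through.** The endpoint has no figure to reproduce. The protocol's only comparative power statement (section 7.1: 95% power for 75% vs. 25%, 20 vs. 20) concerns the second primary outcome and has no bearing here. The check is therefore a comparison of what the endpoint needs with what the protocol collects.

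1. **Sampling occasions per donor.** The flowchart marks sample collection at t1 only, and section 4.1 places the study blood at the procedure. Count: one.

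2. **Later patient outcomes.** The flowchart has no column after t1. From 07/2024 to 07/2026 is 24 months, which the Gantt shows as months 37-60. The rows marked in that period are hepatocyte differentiation, stellate-cell work, assembloid generation, in vitro treatment, PNPLA3 silencing and data correlation. None is a patient visit, repeat biopsy or outcome collection. Section 3.2 requires clinical data to be available but does not say that they extend beyond the procedure. Planned outcome follow-up: none.

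3. **Comparison across stages.** Section 7.1 wants normal liver, inflammation/fibrosis and HCC represented. With one occasion per donor, no donor is observed moving from one stage to the next. Paired intra- and extra-tumoral tissue from an HCC donor (section 4.1) is collected at the same operation, so it does not order events in time either.

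4. **What can be estimated in patients.** With one marker value per donor and no subsequent event, a hazard ratio, a time-dependent AUC or a predictive value for progression cannot be calculated. The association of the marker with the stage present at sampling can be.

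5. **What can be estimated in vitro.** Section 4.5 exposes assembloids to fatty acids and other insults, reads lipid content and stellate-cell activation at 36 hours, and reads morphology, biomarkers and fibrotic status at 120 hours. Silencing (section 4.5) and CRISPR-Cas9 (Secondary Endpoints) add experimental perturbation. This evidence is ordered in time, but within the model.

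6. **Endpoint against objective.** Section 2.2 says identification, with validation to follow elsewhere. The endpoint says predictive. The endpoint is the broader of the two, and steps 1 to 4 show that the design reaches only the narrower one.

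7. **Setting of the blood draw.** By procedure, suspected NASH and post-transplant healthy livers are sampled at biopsy; HCC, other lesions and cholecystectomy at surgery. Section 4.1 does not say whether the draw precedes sedation, anaesthesia or tissue removal. Stage and setting overlap only in part, and no donor counts by procedure are given, so the degree of overlap cannot be calculated.

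**The case against.** The strongest reply is that this is mainly a laboratory study. It induces the phenotype, reads it at two times and perturbs it, so it does give time-ordered experimental evidence. That stands. A reader might infer that the whole design yields nothing beyond cross-sectional association; the documents do not support this, and the limit applies to donors only. It does not rescue the endpoint wording, because section 2.2 seeks non-invasive markers for risk stratification of individuals, and a culture response over 120 hours does not show that a marker predicts a patient's course.

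A second reply is that section 2.2 already describes discovery with later validation, and that no prediction model or accuracy claim is planned. This also stands, and it makes the matter one of wording. It is equally the reason for the endpoint to match its objective.

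Three stronger readings are not supported:

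- A reader might take section 9 ("resolve the temporal order of events that regulate its evolutionary trajectory") as a claim about order of events in patients. That section speaks of the potential of the results and does not tie temporal order to patients.
- A reader might try to size the problem by counting progression events in routine records to study end. The protocol plans no such follow-up and gives no progression rate, so any count would describe another study.
- A reader might infer that HCC or metastasis donors serve as the normal reference for circulating markers. Section 3.2 mentions such resections as a source of healthy liver tissue; nothing makes these donors the reference for blood.

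On the draw, it is fair to say that a laboratory manual may fix the moment, and that the protocol offers no evidence of an anaesthetic effect on these markers. The request is a cheap precaution and does not rest on a demonstrated bias.

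**Conclusion.** The point holds, limited to patients. The endpoint exceeds both its own objective and the design: one sampling occasion per donor and no planned outcome follow-up, hence no estimable patient-level measure of prediction. This rests on reading the undefined clinical data of section 3.2 as not including later outcomes, since nothing in the protocol says that they do. It is not something a statistical analysis plan could repair, because the observations would not exist. The consequence is confined to what may be concluded from one secondary endpoint. The primary endpoints, the sample size and the risk to donors are unaffected. The timing of the blood draw is a secondary matter whose size cannot be stated from the document.

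**What to change.** Reword the secondary endpoint along these lines: *identification of candidate biomarkers associated cross-sectionally with disease stage in donors, and with the induced steatohepatitis phenotype and stellate-cell activation in vitro, for subsequent validation in clinical series*. This brings it into line with section 2.2.

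In section 4.1, state that the study blood sample already planned is drawn at the same pre-procedure moment in all donors, before sedation or anaesthesia and before tissue removal.

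The cost is protocol wording, a more modest claim and a fixed draw time. No additional visits, samples or donors are needed.
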